# Part 1 (24-week evaluation of blinded efficacy and safety data)

Subjects with HAE Type 1 or 2 will be eligible for the study following assessment of data obtained from screening procedures, including demonstration of a minimum number of attacks

documented during a prospective run-in period of 2 to 8 weeks from the date of the screening visit.

Approximately 96 treatment-eligible subjects will receive study drug (BCX7353 or placebo) in Part 1 of the study based on randomization in a 1:1:1 ratio into 1 of 3 treatment groups:

Group 1 (N = 32): BCX7353 110 mg administered orally QD for 24 weeks

Group 2 (N = 32): BCX7353 150 mg administered orally QD for 24 weeks

Group 3 (N = 32): Placebo administered orally QD for 24 weeks

Enrollment into treatment groups will be stratified by the baseline HAE attack rate ( $\geq 2$  attacks/month vs. < 2 attacks/month).

Qualifying attacks for eligibility determination are characterized as follows:

- The attacks must occur during the run-in period of 56 consecutive days, starting on the day of the screening visit
- The attacks are unique, defined as an attack that does not begin within 48 hours of the end of a previous attack.
- The attacks must have either been treated, required medical attention, or be documented to cause functional impairment, based on the subject's entry in the electronic diary (e-diary). Functional impairment is defined as the subject not being able to perform his or her daily activities without restriction (ie, subject records that he/she is at least slightly restricted in daily activities during the HAE attack).
- The attacks must include symptoms of swelling. Symptoms of swelling, in addition to visible swelling, may also include symptoms in the oropharyngeal or abdominal regions, which are indicative of internal swelling.
- The attacks are otherwise confirmed by the Investigator to be HAE attacks.

Once the subject records 2 such attacks, he or she may be randomized to study drug beginning on or after Day 28 of the run-in period; subjects who have at least 3 such attacks may be randomized to study drug beginning on or after Day 14 of the run-in period. A study schematic can be found in Figure 1.

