## 6.6.1. Baseline Attack Rate

Enrollment into treatment groups is stratified by the baseline HAE attack rate as determined by the IXRS system based on the number of attacks and duration of screening as input by the sites ( $\geq 2$  attacks/month vs. < 2 attacks/month). For analysis purposes, the baseline attack rate will be calculated from the diary data and expressed as attacks per month where 1 month = 28 days as follows:

Number of HAE attacks meeting baseline criteria from Screening to First Dose Date/time × 28

Date of First Dose – Screening Date + 1

Criteria that must be met for attacks to qualify for confirmation by the Investigator during the baseline period are provided in Section 4.1.

Baseline attack rate will be included in statistical models as appropriate.

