#### **Confirmed Attack Rate**

Confirmed attack rates will be computed based on the number of confirmed attacks that occur during the reporting period of interest.

Confirmed attack rates will be computed for the following reporting periods and expressed in units of attacks/month where 1 month = 28 days:

- Parts 1 and 2, By month
- Parts 1 and 2, Entire dosing period
- Parts 1 and 2, Effective dosing period

Confirmed attack rates will be computed for Part 1 and at the end of Part 2. For confirmed attack rates by month, months will be defined in blocks of 28 days, beginning on Day 1, the day of first dose. The entire dosing period begins on Day 1 or adjusted Day 1 during Part 2 for subjects originally randomized to placebo. The effective dosing period similarly begins on Day 8 or adjusted Day 8. Part 1 continues until the time of Part 2 dose. Part 2 continues until the time of first dose for Part 3. Investigator confirmation is not done in Part 3 and so confirmed attack rate

will not be computed for Part 3. If the subject discontinues treatment early, the reporting period will continue through 24 hours post last dose and any attacks that occur within 24 hours after last dose will be counted in the calculation of attack rate. If there are confirmed attacks in the eCRF without corresponding diary information, as may happen if a subject verbally reports an attack to an investigator but does not enter it into the ediary, the attack will be counted.

For sensitivity analyses for missing data for the Part 1 primary analysis, confirmed attack rates for the entire dosing period for subjects who discontinue treatment early will be re-computed as a weighted average of the observed post-treatment discontinuation attack rate and an imputed attack rate for periods of missing data post-treatment discontinuation. Details are provided in Section 6.8.1.

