### **Adjusted Confirmed Attack Rate**

An adjusted confirmed attack rate will be computed for use in the determination of the 50% responder endpoint comparing post-baseline attack rates to baseline attack rates. For the adjusted confirmed attack rate, the 2 additional requirements for confirmation of attack rates used during screening will be applied to post-baseline confirmed attacks to determine the number of confirmed attacks meeting the additional requirements. The additional requirements are:

- The attacks are unique, which is defined as an attack that does not begin within 48 hours of the end of a previous attack.
- The attacks must have either been treated, required medical attention or be documented to cause functional impairment based on subject entry in the diary. Functional impairment is defined as the subject being unable to perform their daily activities without restriction (ie, subject records that they are at least slightly restricted in their daily activities during their HAE attack).

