# 8.6. Analysis of the Primary Efficacy Endpoint

## 8.6.1. Primary Efficacy Analysis

The primary efficacy endpoint for Part 1 of the study is the rate of investigator-confirmed HAE attacks during dosing in the entire 24-week treatment period during Part 1 (Day 1 to first dose of Part 2). The first dose in Part 2 is expected on Day 169. The primary efficacy analysis will be produced using the ITT population. The estimand will be based on data from subjects who are on study treatment and this analysis will not include data post treatment discontinuation.

The number of investigator-confirmed HAE attacks for Part 1 will be analyzed by treatment group using appropriate descriptive statistics for the confirmed attack rate (expressed as attacks/month) based on the 24-week dosing period or until study treatment discontinuation, if applicable. An additional summary of confirmed attack rate by month, including change from baseline attack rate and percentage change from baseline attack rate by month, will be produced. The primary efficacy analysis will be conducted using Part 1 data and the primary efficacy endpoints will be summarized and listed by Part 1 treatment group.

The attack rate and the treatment comparisons between each BCX7353 dose and placebo in the rate of investigator-confirmed HAE attacks during the Part 1 dosing period will be analyzed using a Poisson regression model. The number of investigator-confirmed attacks will be included as the dependent variable, the treatment will be included as a fixed effect, the stratification variable (baseline attack rate) will be included as a covariate and the logarithm of duration on treatment will be included as an offset variable. The estimated rate of attack for each treatment group, the treatment differences expressed as the attack rate ratio (BCX7353 over placebo rate ratio) and their associated 95% confidence intervals (CIs) will be provided from the Poisson regression model. The percentage reduction from placebo will be calculated for each dose as:

Rate reduction = 
$$1 - \text{attack rate ratio} = 1 - \frac{R_A}{R_P}$$

Where  $R_P$  is the estimated attack rate for Placebo treatment and  $R_A$  is the estimated attack rate for Active treatment.

Example SAS pseudo-code for the Poisson regression analysis is as follows:

```
proc genmod data = datasetname;
class trt01p catblatk/param=glm;
model icattacks = trt01p catblatk /dist=poisson link=log offset=logdurtrt;
run;
```

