#### Figures

Output #	Population Title	Output Title
14.1.1.2	All Subjects	CONSORT Diagram, Part 1
14.1.1.2.ES	All Subjects	CONSORT Diagram, Entire Study
14.1.5.2	Safety	Plot of Duration of Exposure to Study Drug, Part 1
14.1.5.2.ES	Safety	Plot of Duration of Exposure to Study Drug, Entire Study
14.2.1.7	ITT	Box Plot of Individual Investigator-Confirmed Attack Rate for Entire Dosing Period, Part 1
14.2.1.7.ES	ITT	Box Plot of Individual Investigator-Confirmed Attack Rate for Entire Dosing Period, Entire Study
14.2.1.8	ITT	Cumuative Distribution Plot of Individual Investigator-Confirmed Attack Rate for Entire Dosing Period, Part 1
14.2.1.8.ES	ITT	Cumulative Distribution Plot of Individual Investigator-Confirmed Attack Rate for Entire Dosing Period, Entire Study
14.2.1.9	ITT	Forest Plot of Results of Sensitivity Analyses of Investigator-Confirmed Attack Rate for Entire Dosing Period, Part 1
14.2.1.10	ITT	Forest Plot of Results of Subgroup Analyses of Investigator-Confirmed Attack Rate for Entire Dosing Period, Part 1

Output #	Population Title	Output Title		
14.2.1.12	ITT	Box Plot of Individual Investigator-Confirmed Attack Rate for Effective Dosing Period, Part 1,		
14.2.1.12.ES	ITT	Box Plot of Individual Investigator-Confirmed Attack Rate for Effective Dosing Period, Entire Study		
14.2.1.13	ITT	Cumulative Distribution Plot of Individual Investigator-Confirmed Attack Rate for Effective Dosing Period, Part 1		
14.2.1.13.ES	ITT	Cumulative Distribution Plot of Individual Investigator-Confirmed Attack Rate for Effective Dosing Period, Entire Study		
14.2.2.2	ITT	Histogram Plot of Baseline Investigator-Confirmed Attack Rate, Part 1		
14.2.2.3	ITT	Plot of Mean Investigator-Confirmed Attack Rate by Month, Part 1		
14.2.2.3.ES	ITT	Plot of Mean Investigator-Confirmed Attack Rate by Month, Entire Study		
14.2.2.3.P3	ITT	Plot of Mean Subject-Reported Attack Rate by Month, Part 3		
14.2.2.4	ITT	Plot of On-Study Investigator-Confirmed Attack Rate vs Baseline Investigator-Confirmed Attack Rate, Part 1		
14.2.2.4.ES	ITT	Plot of On-Study Investigator-Confirmed Attack Rate vs Baseline Investigator-Confirmed Attack Rate, Entire Study		
14.2.2.5	ITT	Plot of Difference Between On-Study Investigator-Confirmed Attack Rate and Baseline Investigator-Confirmed Attack Rate vs Baseline Investigator-Confirmed Attack Rate, Part 1		
14.2.2.6	ITT	Plot of Change from Baseline Attack Rate Versus Percent Compliance, Part 1		
14.2.3.3	ITT	Plot of Mean AE-QoL Scores Over Time, Part 1		

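### Monthly change from baseline and Figures 14.2.2.4 to 14.2.2.6 compare a baseline attack rate under two extra criteria with an on-treatment rate that lacks them, so they are not like for like

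*SAP*

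**What the plan says.** The point rests on the SAP for BCX7353-302. The protocol supplied is for a different study (BCX7353-202), so the 302 protocol could not be checked.

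- **Baseline rate (SAP 6.6.1).** The numerator is "Number of HAE attacks meeting baseline criteria from Screening to First Dose Date/time", and the reader is sent to section 4.1 for the criteria. Two of these matter here: "The attacks are unique, defined as an attack that does not begin within 48 hours of the end of a previous attack", and "The attacks must have either been treated, required medical attention, or be documented to cause functional impairment".
- **On-treatment rate (SAP 6.7.5.1, Confirmed Attack Rate).** "Confirmed attack rates will be computed based on the number of confirmed attacks that occur during the reporting period of interest". Section 4.1 requires every confirmed attack to include swelling symptoms. It states no 48-hour rule and no treatment, attendance or impairment rule for attacks after baseline.
- **Adjusted rate (SAP 6.7.5.1, Adjusted Confirmed Attack Rate).** For the 50% responder endpoint, "the 2 additional requirements for confirmation of attack rates used during screening will be applied to post-baseline confirmed attacks". The relative-reduction formula in 6.7.5.4 and Tables 14.2.6.1.1 (ITT) and 14.2.6.1.2 (PP) use this rate.
- **Displays at issue.** The monthly summary in 8.6.1 (Table 14.2.2.1), "including change from baseline attack rate and percentage change from baseline attack rate by month", is attached to the unadjusted confirmed rate. Figures 14.2.2.4 (on-study against baseline rate), 14.2.2.5 (difference against baseline rate) and 14.2.2.6 ("Plot of Change from Baseline Attack Rate Versus Percent Compliance, Part 1") also compare with baseline, and nothing in the SAP applies the adjusted rate to them.

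**The concern.** A change from baseline is interpretable only if the same events are counted before and after. Here some attacks that count on treatment would not have counted in the run-in. The SAP recognises this for the responder endpoint and corrects it there, but gives no reason for leaving the same comparison uncorrected by month and in the three figures.

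At stake is the description of how far each arm moved from its own baseline. The clinical study report could carry two different reductions from baseline for one arm, one from Table 14.2.2.1 and one from Table 14.2.6.1.1, with no planned explanation. The title of Figure 14.2.2.4 uses the term investigator-confirmed for both rates, so a reader could not see that two definitions are in play.

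**Working it through.** The SAP gives no figure on this point to reproduce. Its sample-size calculation (4.3.1) does not involve a comparison with baseline.

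**Step 1: direction.** The adjusted rate adds requirements to the confirmed rate. The confirmed on-treatment count is therefore equal to or higher than the count under the baseline definition, never lower. Taken alone, the mismatch can only make a reduction look smaller or an increase look larger.

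**Step 2: size.** Let B be the baseline rate, d the true like-for-like reduction, and q the share of on-treatment confirmed attacks that fail either extra requirement. The documents do not give q; 0 to 30% is an assumed range, taken as equal in all arms.

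- On-treatment rate under the baseline definition: B(1 − d)
- On-treatment confirmed rate: B(1 − d)/(1 − q)
- Change as planned: (1 − d)/(1 − q) − 1

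Worked example at q = 10%: with d = 50%, 0.5/0.9 − 1 = −44.4%; with d = 0, 1/0.9 − 1 = +11.1%.

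| q | True 50% reduction shows as | No true change shows as | Gap between the two (points) |
|---|---|---|---|
| 0% | 50.0% | 0% | 50.0 |
| 5% | 47.4% | +5.3% | 52.6 |
| 10% | 44.4% | +11.1% | 55.6 |
| 20% | 37.5% | +25.0% | 62.5 |
| 30% | 28.6% | +42.9% | 71.4 |

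With equal q the ratio of the two on-treatment rates stays at 0.50, but the gap in percentage change widens. The distortion is therefore not simply conservative. If q differs between arms, so does the distortion.

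On the absolute scale, take an assumed baseline of 3 attacks per month and q = 10%. No true change shows as 3/0.9 − 3 = +0.33, and a true halving shows as 1.5/0.9 − 3 = −1.33 instead of −1.50.

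**Step 3: check of the algebra.** A Poisson simulation at 3 attacks per month and q = 10% gave a rise of 11.1% with no true change and a reduction of 44.4% for a true halving. Counting on-treatment attacks under the baseline definition returned 0% and 50%.

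**Step 4: an opposing influence.** Section 4.1 allows randomization from Day 28 once 2 qualifying attacks are recorded, or from Day 14 once there are 3. That selects subjects on attacks during the run-in and stops the run-in after them, which raises the mean baseline rate. A simulation assumed a constant Poisson rate, q = 0, an inert treatment, and randomization on the earliest permitted day or 14 days later. The group mean rate changed as follows:

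| True attacks per month | Earliest permitted day | 14 days later |
|---|---|---|
| 2 | −28% | −16% |
| 3 | −20% | −9% |
| 4 | −15% | −6% |

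Combining both at 3 per month and q = 10%: 0.80/0.9 = 0.89, a fall of 11%; or 0.91/0.9 = 1.01, a rise of 1%. The net sign depends on quantities that the documents do not give.

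These figures concern group mean rates. SAP 6.7.2 defines percentage change as change divided by baseline. If that is averaged over subjects, division by a short, noisy baseline pushes the average up and can offset part of the run-in effect.

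**The case against.** Much of the opposing case stands.

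- **No inference is touched.** Section 8.6.1 calls the monthly table an additional summary, and it is descriptive. The primary percentage reduction is one minus the active-to-placebo rate ratio, with one attack definition in every arm and baseline only as a covariate. Apart from the responder analysis, no change from baseline in attack rate is a Part 1 endpoint or enters the testing hierarchy in 8.5.
- **The main comparison with baseline is already correct.** The responder endpoint uses the adjusted rate, and Tables 14.2.6.1.1 and 14.2.6.1.2 report the overall Part 1 reduction on it.
- **q may be small.** Even slight restriction of daily activities satisfies the impairment rule, and 6.7.5.5 lets investigators merge several reported attacks into one.
- **Replacing the confirmed rate has a cost.** The monthly table would then count different attacks from the primary endpoint and from the monthly mean plot.

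A reader might infer that the reported reductions are wrong in every arm. The documents do not support that, because q is not given and could be zero. Nor do they support a prediction that placebo will appear to worsen, because run-in selection may act in the opposite direction. It would also be wrong to infer from the section title that the primary efficacy result is biased.

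None of this explains why one comparison with baseline is made under matched definitions and the others are not. The consistency objection is met by keeping both rates.

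**Conclusion.** The point holds as a minor one. The monthly change and percentage change columns and Figures 14.2.2.4 to 14.2.2.6 compare rates under two attack definitions. The mismatch alone understates the reduction in any arm where some on-treatment confirmed attacks fail the 48-hour rule or the treated, attended or impairing rule. For illustration, q = 10% turns a true 50% reduction into 44% and no change into +11%; at q = 0 nothing changes. Those figures assume equal q in all arms, refer to group mean rates, and set aside the run-in selection. The direction of the mismatch is certain; its size and the net direction of the displayed change are not. The primary Poisson rate ratio, the responder endpoint and the overall Part 1 reduction in Tables 14.2.6.1.1 and 14.2.6.1.2 are unaffected.

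**What to change.** Before Part 1 is unblinded, amend SAP 8.6.1 and the display specifications as follows:

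1. Compute the monthly change and percentage change columns of Table 14.2.2.1 with the adjusted confirmed attack rate of 6.7.5.1.
2. Use the same adjusted rate for the on-treatment values in Figures 14.2.2.4, 14.2.2.5 and 14.2.2.6.
3. Keep the unadjusted confirmed rate by month in the table, for description between arms and consistency with the primary endpoint and the monthly mean plot.
4. Add a footnote to each display stating which attack definition applies to the baseline rate and which to the on-treatment rate.
5. Apply the 48-hour rule to each subject's full sequence of attacks before splitting it into 28-day months, so that a month boundary does not turn one attack into two.

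The cost is a small amount of programming. The adjusted rate is already planned over Part 1 for the responder endpoint and can serve the figures; the version by month is new. No new data are needed and no test changes.

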#### Statistical methods:

The primary endpoint is the rate of investigator-confirmed HAE attacks during dosing in the entire treatment period of Part 1, expressed as attacks per month where 1 month is defined as 28 days. Comparisons of the rate of investigator-confirmed HAE attacks between each BCX7353 dose and placebo during the entire dosing period for Part 1 will be conducted using a Poisson regression model. The number of investigator-confirmed attacks will be included as the dependent variable, the treatment will be included as a fixed effect, baseline attack rate will be included as a covariate and the logarithm of duration on treatment will be included as an offset variable. The estimated monthly rate of attacks for each treatment group, the treatment differences expressed as the attack rate ratio (BCX7353 over placebo rate ratio) and their associated 95% confidence intervals (CIs) will be provided from the Poisson regression model.

Missing data sensitivity will be conducted for the analysis of the primary endpoint using data collected post treatment discontinuation and using multiple imputation for missing data, In addition, a a tipping point analysis will be conducted. A separate analysis using only data from subjects who completed Part 1 will also be conducted.

Analysis of secondary endpoints for Part 1 will be as follows:

Treatment comparisons in the AE-QoL total score change from baseline will be analyzed using a mixed model for repeated measures (MMRM) with fixed effects for treatment, baseline attack rate, baseline AE-QoL, visit, a visit by treatment interaction, and a random effect for subject. An unstructured covariance structure will be used. The estimated treatment difference for each BCX7353 dose vs. placebo at each visit will be displayed together with the 95% CI and the associated p-value. Primary inferences will be drawn from treatment differences for the changes from baseline derived from the MMRM model at Week 24. The change from baseline in the AE-QoL domain scores (function, fatigue, nutrition, and fear/shame) will also be analyzed using the MMRM model.

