# 4.3. Sample Size Considerations

# 4.3.1. Sample Size Justifications

The pooled standard deviation (SD) of the attack rate during effective dosing period (Days 8 to 28) in Study BCX7353-203 was 0.55. The observed treatment difference between the BCX7353 125 mg dose with dihydrochloride salt (equivalent to the 110 mg free base dose for the current study) and placebo for the effective dosing period using the full analysis population was 0.70 attacks/week, which represented a 73.8% reduction in attack rate from the placebo group.

Assuming a normalized placebo attack rate of 1 unit and a common SD of 0.55 units for BCX7353 and placebo attack rates, a sample size of 32 subjects will have 94% power to detect a 50% attack rate reduction (a treatment difference of 0.5 units) between BCX7353 and placebo, based on a 2-sided test at significance level of 0.05.

Sample sizes were increased to approximately 40 subjects for each active treatment group and placebo, to conservatively account for a potential dropout rate of 20%. Initial sample size calculations at the time the protocol was written did not allow for dropout.

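### The Study 302 primary model adjusts for baseline attack rate only as a two-level category; adding the exact rate costs one term and may sharpen the estimate

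*SAP*

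**What the plan says.** The SAP supplied is for Study 302; the protocol supplied is for Study 202, so the 302 protocol's description of the model could not be checked. Within the SAP:

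- **Synopsis, Statistical methods:** for the primary Poisson model, "baseline attack rate will be included as a covariate".
- **6.6.1:** defines the baseline attack rate as a calculated quantity, qualifying attacks from screening to first dose times 28 over days elapsed, and adds: "Baseline attack rate will be included in statistical models as appropriate".
- **6.6.2:** defines the categorized baseline attack rate separately, as that calculated rate cut at 2 per month.
- **8.6.1, text:** "the stratification variable (baseline attack rate) will be included as a covariate".
- **8.6.1, example code:** "model icattacks = trt01p catblatk /dist=poisson link=log offset=logdurtrt", with `catblatk` also listed in the CLASS statement. The SAP does not define `catblatk`, but its name, the CLASS statement and the text all point to the two-level category.
- **8.7.3:** the effective-period rate is analyzed in a similar way.
- **8.7.1 and 8.7.2:** the AE-QoL and symptom-day models name the baseline attack rate, with no mention of a category.
- **8.6.2:** no sensitivity analysis uses the exact rate.

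**The concern.** There are two linked problems. First, the synopsis read with 6.6.1 and 6.6.2 points to the uncut rate, while 8.6.1 points to the category. Two analysts could fit different primary models, both defensibly.

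Second, the version in the code uses less of the information. A subject at 2.1 attacks per month and one at 8 per month get the same covariate value. Variation in the baseline rate within each stratum stays in the residual. It adds to the extra-Poisson variation that 8.6.1 itself worries about, and chance imbalance within strata goes uncorrected with about 40 subjects per arm. The category and the exact rate each use one degree of freedom, so the cut saves nothing. At stake is the efficiency of the primary rate ratio, not its validity.

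**Working it through.** **1. The plan's own figure.** SAP 4.3.1 claims that "a sample size of 32 subjects will have 94% power to detect a 50% attack rate reduction". Its inputs are a placebo mean of 1 and an SD of 0.55 in both groups (normalized units), a difference of 0.5, and two-sided alpha 0.05. Normal approximation: z = 0.5/(0.55 × √(2/32)) − 1.96 = 0.5/0.1375 − 1.96 = 1.676, giving 95.3% power. The noncentral t gives 94.7%. The stated 94% is therefore reproduced, as is 32/0.8 = 40 per arm after 20% dropout. No covariate enters this calculation, so the covariate's form cannot move it.

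**2. A plausible placebo rate.** SAP 4.3.1 reports that the Study 203 difference "was 0.70 attacks/week, which represented a 73.8% reduction in attack rate from the placebo group". Hence 0.70/0.738 = 0.949 per week, or 3.79 per 28 days.

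**3. Why the planned standard error does not respond.** With the Poisson scale fixed at 1, Var(log RR) ≈ 1/E₀ + 1/E₁, where E₀ and E₁ are total attacks per arm. At 3.8 per 28 days over 6 such months, 40 per arm and a rate ratio of 0.5: E₀ = 3.8 × 6 × 40 = 912 and E₁ = 456. The SE is √(1/912 + 1/456) = 0.057. Event counts fix this value and the covariate barely enters.

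**4. Category versus log rate: simulation.** 1,500 runs per scenario, 40 per arm, 24 weeks, the run-in rule of SAP 4.1, randomization stratified at 2 per month, and log-normal subject rates. *Assumptions, because the documents do not give them:* the between-subject CV², and the share of between-subject log variance that persists from run-in to treatment. Here the log rate **replaces** the category. The SDs of log RR and the unscaled SEs are at a rate ratio of 0.5; the last column is power at 0.7 with a Pearson-scaled SE.

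| Placebo rate | CV² | Persistence | SD, category | SD, log rate | Variance ratio | Unscaled SE, category / log | Scaled power at 0.7 |
|---|---|---|---|---|---|---|---|
| 3.8 | 0.26 | 0.5 | 0.130 | 0.127 | (0.127/0.130)² = 0.95 | 0.057 / 0.057 | 84.1% → 86.6% |
| 2.5 | 0.26 | 0.8 | 0.125 | 0.119 | 0.91 | 0.069 / 0.070 | 85.3% → 87.8% |
| 3.8 | 0.26 | 0.8 | 0.118 | 0.108 | 0.84 | 0.057 / 0.057 | 86.5% → 92.2% |
| 3.8 | 0.50 | 0.8 | 0.151 | 0.133 | 0.78 | 0.056 / 0.057 | 68.3% → 78.6% |

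Each SD carries about 2% Monte Carlo error, so the smallest differences are near noise. At a rate ratio of 0.5, scaled power is at least 99% with either covariate. In these four scenarios the category gave the same SD as no covariate at all. That is expected: stratified randomization already balances it, and 63% to 79% of subjects fall in the upper stratum.

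**5. Log rate added beside the stratum term (the change proposed here).**

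- CV 0.35 to 0.6: variance 0.77 to 0.93 times the planned value. Pearson dispersion fell in every scenario (for example 7.6 to 5.8), and the unscaled SE was unchanged (0.052 both ways). Scaled power at a rate ratio of 0.7 rose by up to about 11 points but was unchanged in one scenario.
- CV 0.3 to 0.45, with drift between run-in and treatment: 0.84 to 1.03.
- Negative binomial model, rate ratio 0.6, CV 0.55 to 0.6: the reported SE fell 6% to 9% (for example 0.128 to 0.116) and the empirical variance fell 11% to 22%.

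**6. Over-dispersion.** In the step 4 scenarios under a true null, the unscaled Poisson test rejected in 35% to 54% of runs with the category and 32% to 49% with the log rate.

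**The case against.** The strongest reply is that nothing in the planned primary output improves: the unscaled Poisson interval keeps its width (step 3), and power at the design effect is already very high. This stands. It does not remove the point, because the estimate itself still varies more around the truth than it need. Moreover, 8.6.1 keeps the Poisson model as primary only if the negative binomial fit agrees and its dispersion parameter is not significant. With heterogeneity of the size simulated, the negative binomial result will matter, and there the gain is visible.

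The gain may also be small. If the Study 203 SD of 0.55 is in attacks per week (its unit is not stated), pure Poisson noise over the three weeks of Days 8 to 28 would give √(0.949/3) = 0.56. True between-subject variation could then be modest, and the gain near zero. This stands too, and sets the lower end of the range.

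The stratum term reflects the stratified design and assumes no log-linear shape, and the run-in rate is noisy because entry is triggered by attacks. Keeping the stratum term answers the first part. On the second, the rate ratio is collapsible under a log link with randomized treatment, so an imperfect shape costs efficiency rather than changing what the Poisson model estimates.

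Finally, the code is labeled as an example and the synopsis can be read as the uncut rate. That is fair. It makes the inconsistency part of the finding rather than a rebuttal.

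**Conclusion.** By its text and code, 8.6.1 adjusts the primary model only for the two-level category. The exact rate is available for each dosed subject, and the synopsis does not agree with 8.6.1. Adding the log rate is an inexpensive improvement, worth between almost nothing and about 25% of the true variance of the log rate ratio. The size rests on the between-subject CV and on the run-in to treatment correlation, neither of which the documents give.

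Stronger readings that the documents do not support:

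- *That the exact rate is worth a fixed share of the sample, such as 16% to 28%.* Such figures arise only with high rates, CV 0.6 to 0.8 and delayed randomization, and when the log rate replaces the category instead of joining it.
- *That the planned confidence interval would narrow.* It would not, with the Poisson scale fixed at 1.
- *That this cures over-dispersion.* False rejection stays far above 5% (step 6). That problem needs its own fix.
- *That the AE-QoL and symptom-day models share the fault.* They name the baseline attack rate, which 6.6.1 defines as the uncut rate.
- *That every ITT subject has the exact rate.* The formula needs a first-dose date, and ITT (6.5.3) includes undosed subjects. Those subjects also have no treatment time for the offset.

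**What to change.** Before unblinding Part 1:

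1. In 8.6.1 and 8.7.3, keep the stratum term and add the log of the calculated baseline attack rate (6.6.1) as a continuous covariate in both the Poisson and the negative binomial models. In the example code, add a term such as `logblrate` after `catblatk` in the MODEL statement and leave it out of CLASS.
2. Define `catblatk`, and make the synopsis and 8.6.1 describe the same model.
3. In 8.7.1 and 8.7.2, confirm that the baseline attack rate there means the uncut rate.
4. Handle over-dispersion separately, through the choice of variance or model for the primary analysis.

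Items 1 to 3 cost a few sentences, one derived variable and one degree of freedom, with no new data. The log is defined for everyone who met the entry rule, which requires at least two qualifying attacks; state what happens to any subject randomized in error with none. Prespecification matters, because a covariate form chosen after unblinding would not be credible.
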